treatment of patients with metastatic non-small cell lung cancer (NSCLC) whose tumours have EGFR exon 19 deletions or exon 21 (L858R) substitution mutations as detected by an Food and Drug Administration (FDA)-approved test. It was approved in the European Union (EU) on 25 Sep 2013 (trade name Giotrif®) as monotherapy indicated for the treatment of EGFR TKI-naïve adult patients with locally advanced or metastatic NSCLC with activating EGFR mutation(s). On January 12, 2018, FDA granted approval to afatinib for a broadened indication in first-line treatment of patients with metastatic NSCLC whose tumours have non-resistant EGFR mutations as detected by an FDA-approved test ([P19-04170](#)). Approval was based on demonstration of durable responses in a subset of 32 afatinib-treated patients with metastatic NSCLC harbouring non-resistant EGFR mutations (S768I, L861Q, and/or G719X) other than exon 19 deletions or exon 21 L858R substitutions enrolled in one of three clinical trials (LUX-Lung 2 [NCT00525148], LUX-Lung 3 [NCT00949650], and LUX-Lung 6 [NCT01121393]). The confirmed overall response rate, as assessed by independent radiology review, was 66% (95% confidence interval 47, 81). Among the 21 responders, the proportion of patients with response duration of ≥ 12 months was 52% and the proportion with response durations of ≥ 18 months was 33%. Clinical benefit was lower in patients with de-novo Thr790Met and exon 20 insertion mutations. ([P15-05932](#))

Gefitinib (IRESSA®) and erlotinib (Tarceva®) are first generation EGFR-TKIs and approved by EMA as monotherapy for the treatment of adult patients with locally advanced or metastatic non-small cell lung cancer (NSCLC) with activating mutations of EGFR-TK. FDA label is restricted to common mutations (Del19 and L858R).

Anecdotal data from erlotinib/gefitinib trials show variable and mainly limited responses to EGFR TKIs in a multitude of other EGFR mutations, eg, in Exons 18-21 or a combination of ≥ 2 EGFR mutations ([P16-09907](#)) Post-hoc analyses from the NEJ002 study comparing gefitinib with chemotherapy showed that patients with uncommon EGFR mutations had a significantly shorter OS (11.9 versus 29.3 months; $p < 0.001$). By contrast, OS was similar for uncommon mutations and common mutations in the CarboPac group ($n = 111$; 22.8 versus 28 months; $p = 0.358$) ([R19-1656](#)).

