Only patients with Number of NSCLC treatment lines (as defined before) > 1 and [**MUT2. MUT2_reeval_stop**] = "Yes" will be considered.

Time on treatment with index therapy EGFR-TKI for UNCOMMON MUTATIONS COHORT

The following patients will be considered as having the event “treatment discontinuation”:

- patients with discontinuation of index EGFR-TKI treatment, ie. those with discontinuation defined as “Treatment discontinued?” [EAD. EAD_treat_disc] = “Yes” in the latest record of the EGFR-TKI ADMINISTRATION DETAILS form referred to the index EGFR-TKI treatment (as defined before). For these patients, the time to event will be computed as the difference between the field “Stop date with this dose” [EAD. EAD_stop_date] of the above-mentioned record and the start date of the Index EGFR-TKI therapy (as defined before) + 1 day;
- deceased patients at time of inclusion in the study, ie. those with [PI. PI_pt_class] = “Deceased patient”. For these patients, the time to event will be computed as the difference between the “Date of death” [PI. PI_date_death] and the start date of the Index EGFR-TKI therapy (as defined before) + 1 day.

The same patient could have multiple events, but for the purpose of the analysis only the earliest event will be considered.

Other patients will be considered as censored observations. The following situations might be observed:

- non-deceased patients with evidence of ongoing treatment at end of observation, ie. those with [PI. PI_pt_class] = (“Living patient” OR “Untraceable patient”) and with “Treatment discontinued?” [EAD. EAD_treat_disc] = “No” in the latest record of the EGFR-TKI ADMINISTRATION DETAILS form referred to the index EGFR-TKI treatment (as defined before). For these patients, the time to censoring will be computed as the difference between the end of observation date (as defined later) and the start date of the Index EGFR-TKI therapy (as defined before) + 1 day;

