4 CONTENTS

The analyses will be performed on the Analysis set specified for each table.

Missing data will not be imputed and so patients with missing data will be excluded from the analyses of that variable(s).

If the investigator is unable to collect the requested information the data will be “NK” (Not Known) or “NA” (Not Available), if the investigator did not record the information the data will be “Not Recorded”.

The UPSWING study has descriptive objectives and no specific comparison will be performed. The estimation of confidence intervals limits will be performed, where relevant.

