- absolute and relative frequency of patients achieving Overall Response (ORR), ie. those with [*First-line treatment period / RESP. RESP_best*] = “Complete response (CR)” or “Partial Response (PR)”;
- descriptive statistics (mean, standard deviation, quartiles, min, max) of Duration of response (in months) [*First-line treatment period / RESP. RESP_dur_num, RESP_dur_unit*] for patients achieving Overall Response (ORR) (as defined before); all units will be reported to months.

Descriptives and percentages will be calculated over the number of ELIGIBLE PATIENTS in the cohort, unless differently specified..

Table 25-UNC. Second-line treatment details (ELIGIBLE PATIENTS of the Uncommon Mutation Cohort)

The table will provide:

- absolute and relative frequency of patients by type of treatment (according to the field [*Second-line treatment period / TREAT. TREAT_ty, TREAT_ty_sp*]), “Immune check-point inhibitors” and “Other immunotherapy” will be grouped together;
- absolute and relative frequency of patients by type of chemotherapy [*Second-line treatment period / TREAT. TREAT_chemo, TREAT_chemo_sp*]]; drug combinations will be shown in case of polychemotherapy regimens;
- absolute and relative frequency of patients undergoing radiotherapy (according to the field [*Second-line treatment period /TREAT. TREAT_radio_YN*]);
- absolute and relative frequency of patients by type of targeted therapy (according to the field [*Second -line treatment period /TREAT. TREAT_targTer, TREAT_targTer_sp*]);
- absolute and relative frequency of patients by type of immunotherapy (according to the field [*Second -line treatment period /TREAT. TREAT_immuno, TREAT_immuno_sp*]).

Descriptives and percentages will be calculated over the number of ELIGIBLE PATIENTS in the cohort, considering only patients with Number of NSCLC treatment lines >1 (see “Computed variables” chapter).

Table 28-UNC. Second-line treatment regimen (ELIGIBLE PATIENTS of the Uncommon Mutation Cohort)

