4.1.5 Time on treatment

Table 36-UNC. Time on treatment with index therapy EGFR-TKI (ELIGIBLE PATIENTS of the Uncommon Mutation Cohort) – Primary objective

The table will provide the Kaplan-Meier estimates of quartiles of time on treatment with index therapy EGFR-TKI (with their 95% Confidence Intervals, using Greenwood's variance estimate) (see "Computed variables" chapter).

Moreover, a Kaplan-Meier survival curve will be provided. The analysis will be represented on a plot having the time to event on the horizontal axis and the percentage of event-free patients on the vertical axis.

Table 37-UNC. Time to second-line treatment failure (ELIGIBLE PATIENTS of the Uncommon Mutation Cohort) – Secondary objective #4

The table will provide the Kaplan-Meier estimates of quartiles of time to second-line treatment failure (with their 95% Confidence Intervals, using Greenwood's variance estimate) (see "Computed variables" chapter).

Moreover, a Kaplan-Meier survival curve will be provided. The analysis will be represented on a plot having the time to event on the horizontal axis and the percentage of event-free patients on the vertical axis.

[figure not shown]
The analysis will be performed on ELIGIBLE PATIENTS in the cohort, considering only patients with Number of NSCLC treatment lines >1 (see "Computed variables" chapter) while excluding those with mutation T790M acquired only at second-line osimertinib start.

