4.2.4 NSCLC treatments

Table 15-SEQ. NSCLC treatment patterns (ELIGIBLE PATIENTS of the Sequencing Cohort)

See corresponding table for the UNCOMMON MUTATION COHORT. However, the results will be focused on the 3rd or subsequent lines (if any), since the whole cohort will have in common the initial pattern “afatinib→osimertinib” by definition.

Table 16-SEQ. Details of first-line EGFR-TKI treatment (afatinib) (ELIGIBLE PATIENTS of the Sequencing Cohort)

The table will provide:

- absolute and relative frequency of afatinib starting daily dose (mg) (see “Computed variables” chapter).
- descriptive statistics (mean, standard deviation, quartiles, min, max) of Duration of afatinib treatment (see “Computed variables” chapter).

Descriptives and percentages will be calculated over the number of ELIGIBLE PATIENTS in the cohort.

Table 17-SEQ. Response to first-line treatment (afatinib) (ELIGIBLE PATIENTS of the Sequencing Cohort) – Secondary objective #1

See corresponding table for the UNCOMMON MUTATION COHORT.

Table 18-SEQ. Details of second-line EGFR-TKI treatment (osimertinib) (ELIGIBLE PATIENTS of the Sequencing Cohort)

The table will provide:

- absolute and relative frequency of osimertinib starting daily dose (mg) (see “Computed variables” chapter)
- patients’ distribution (absolute and relative frequency) by “Which programme was used for patient treatment with osimertinib?” [[Second-line treatment period / TREAT.TREAT_osim_progr](#)]
- descriptive statistics (mean, standard deviation, quartiles, min, max) of Duration of osimertinib treatment (see “Computed variables” chapter)

Descriptives and percentages will be calculated over the number of ELIGIBLE PATIENTS in the cohort.

Table 19-SEQ. Response to second-line treatment (osimertinib) (ELIGIBLE PATIENTS of the Sequencing Cohort) – Secondary objective #1

See corresponding table for the UNCOMMON MUTATION COHORT.

Moreover, the table will provide patients’ distribution (absolute and relative frequency) by “Presence of brain metastases at the end of osimertinib treatment line?” [[Second-line treatment period / RESP.RESP_brain_met](#)].

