5.2.4 NSCLC treatments

Table 15-SEQ. NSCLC treatment patterns (ELIGIBLE PATIENTS of the Sequencing Cohort)

See corresponding table for the UNCOMMON MUTATION COHORT. However, the results will be focused on the 3rd or subsequent lines (if any), since the whole cohort will have in common the initial pattern “afatinib→osimertinib” by definition.

Table 16-SEQ. Details of first-line EGFR-TKI treatment (afatinib) (ELIGIBLE PATIENTS of the Sequencing Cohort)

ELIGIBLE PATIENTS (N=xxx)		
Afatinib starting daily dose (mg)	50 mg	xxx (xx.x%)
	40 mg	xxx (xx.x%)
	30 mg	xxx (xx.x%)

Duration of afatinib treatment	N	xxx
	Mean	xx.x
	SD	xx.x
	25th percentile	xx.x
	Median	xx.x
	75th percentile	xx.x
	Min	xx.x
	Max	xx.x

Table 17-SEQ. Response to first-line treatment (afatinib) (ELIGIBLE PATIENTS of the Sequencing Cohort) – Secondary objective #1

See corresponding table for the UNCOMMON MUTATION COHORT.

Table 18-SEQ. Details of second-line EGFR-TKI treatment (osimertinib) (ELIGIBLE PATIENTS of the Sequencing Cohort)

ELIGIBLE PATIENTS (N=xxx)		
Osimertinib starting daily dose (mg)	80 mg	xxx (xx.x%)
	40 mg	xxx (xx.x%)
Programme used for patient treatment	Regular Clinical Practice	xxx (xx.x%)
	Through EAP/CUP	xxx (xx.x%)
Duration of osimertinib treatment	N	xxx
	Mean	xx.x
	SD	xx.x
	25th percentile	xx.x
	Median	xx.x
	75th percentile	xx.x
	Min	xx.x
	Max	xx.x

Table 19-SEQ. Response to second-line treatment (osimertinib) (ELIGIBLE PATIENTS of the Sequencing Cohort) – Secondary objective #1

		ELIGIBLE PATIENTS (N=xxx)
Best response achieved	Complete response (CR)	xxx (xx.x%)
	Partial Response (PR)	xxx (xx.x%)
	Stable Disease (SD) or Non-CR/Non PD	xxx (xx.x%)
	Disease Progression	xxx (xx.x%)
	UNK	xxx (xx.x%)
Overall Response (ORR)		xxx (xx.x%)
Duration of response (in months)	N	xxx
	Mean	xx.x
	SD	xx.x
	25th percentile	xx.x
	Median	xx.x
	75th percentile	xx.x
	Min	xx.x
	Max	xx.x
Presence of brain metastases at the end of osimertinib treatment line?	Yes	xxx (xx.x%)
	No	xxx (xx.x%)
	UNK	xxx (xx.x%)

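### Duration of response is summarised without censoring in Tables 24-, 30- and 35-UNC and 19-SEQ, so responses still ongoing at data collection make it look shorter than it is

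*SAP*

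**What the plan says.** SAP section 4.1.4 specifies, for Tables 24-UNC (first line), 30-UNC (second line) and 35-UNC (index line), "descriptive statistics (mean, standard deviation, quartiles, min, max) of Duration of response (in months") among patients with a complete or partial response. The source is the pair of fields "RESP. RESP_dur_num, RESP_dur_unit": a number and its unit. Section 4.2.4 extends this to the sequencing cohort by reference for Tables 17-SEQ and 19-SEQ ("See corresponding table for the UNCOMMON MUTATION COHORT"). The 19-SEQ layout in section 5.2.4 lists "Duration of response (in months") with N, mean, SD, quartiles, minimum and maximum, and has no row for ongoing or censored responses.

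SAP chapter 3 has no algorithm for duration of response. The general rule in chapter 4 is "Missing data will not be imputed and so patients with missing data will be excluded from the analyses of that variable(s").

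The SAP treats its other time-to-event quantities differently. For time on treatment, chapter 3 censors "non-deceased patients with evidence of ongoing treatment at end of observation", and section 4.1.5 states: "The table will provide the Kaplan-Meier estimates of quartiles of time on treatment with index therapy EGFR-TKI". Time to second-line failure and overall survival are handled in the same way.

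**The concern.** Duration of response is a time-to-event quantity: a patient still responding when the chart is read has no final value. The SAP expects patients still on treatment at that point. So does the protocol, which reports only 52% maturity for time to treatment failure in the predecessor sequencing study (section 7.2). Some responders will therefore still be responding.

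With one number and no status, the plan leaves two routes for such a patient. If the field is blank, the chapter 4 rule removes the patient, and only responses that have already ended are summarised. If the duration to date is entered, it counts as a completed response. Sites may mix the two. The longest responses are the ones lost or shortened, so the tables would describe something other than how long responses last, and the result would depend on how recently patients were treated.

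**Working it through.** The documents give no figure for duration of response, so there is none to reproduce. The check is on direction, then on plausible size.

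**Direction.** Let T be the true duration and C the time from response onset to data collection.
- Counted as complete: the recorded value is min(T, C), which never exceeds T.
- Dropped: the summary uses T given T ≤ C. If C is independent of T, each duration u is weighted by P(C ≥ u), which falls as u grows, so long responses are under-represented.

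Neither route can overstate duration. The mean is understated whenever any response is ongoing.

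**Inputs for size.**
- Level: protocol section 7.1 says of 21 afatinib responders that "the proportion of patients with response duration of ≥ 12 months was 52" per cent, and that 33% reached 18 months. Under an exponential model these imply medians of 12 × ln 2 / −ln 0.52 = 12.7 and 18 × ln 2 / −ln 0.33 = 11.3 months. I use 12.
- Minimum follow-up: 11.5 months from index start (SAP section 2.1, criterion 7, uncommon cohort).
- Assumed, not in the documents: exponential durations, onset 2 months after treatment start, follow-up uniform from 11.5 to 36 or 60 months. So C is uniform on (a, b) with a = 9.5 and b = 34 or 58.

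**Formulas**, with λ = ln 2 / 12 = 0.05776 and true mean 1/λ = 17.3:
- Share ongoing p = [exp(−λa) − exp(−λb)] / [λ(b − a)]. For b = 34: (0.5777 − 0.1403) / (0.05776 × 24.5) = 0.309. For b = 58: (0.5777 − 0.0351) / (0.05776 × 48.5) = 0.194.
- Median if dropped (valid while below a): m = −ln[1 − (1 − p)/2] / λ. This gives −ln(0.6545)/0.05776 = 7.3 and −ln(0.5968)/0.05776 = 8.9.
- Median if counted as complete: solve exp(−λt) × (b − t)/(b − a) = 0.5, giving 10.9 and 11.3.
- Mean if counted as complete: (1 − p)/λ = 12.0 and 14.0.

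The remaining cells come from simulation with 400,000 responders per scenario, which also agrees with the formulas above to within 0.1 month.

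| Months | True | Dropped, to 36 | Dropped, to 60 | Counted as complete, to 36 | Counted as complete, to 60 |
|---|---|---|---|---|---|
| Median | 12.0 | 7.3 (−39%) | 8.9 (−26%) | 10.9 (−9%) | 11.3 (−6%) |
| Mean | 17.3 | 8.8 (−49%) | 11.6 (−33%) | 12.0 (−31%) | 14.0 (−19%) |
| Upper quartile | 24.0 | 12.8 (−47%) | 16.6 (−31%) | 17.3 (−28%) | 19.8 (−18%) |

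Kaplan-Meier with ongoing responses censored returns a median of 11.9 to 12.0 in these scenarios.

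**Table 19-SEQ.** Take an assumed true median of 10 months on osimertinib and follow-up from the SAP minimum of 9.5 months to 36. Then 27% are ongoing, and the median is 6.5 if they are dropped and 9.1 if counted as complete. The upper quartile of 20 becomes 11.8 or 15.1.

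**Range.** Over true medians of 8 to 15 months and maximum follow-up of 24 to 60 months in both cohorts, 10–52% of responses are ongoing. Dropping them lowers the median by 14–60%. Counting them as complete lowers it by 0–31%, the mean by 10–51% and the upper quartile by 8–51%.

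**The case against.** Several points on the other side stand.

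- Duration of response is not a protocol outcome. Secondary objective 1 is the response rate, and protocol section 9.3 lists best response but not its duration. The statistic is a supporting line in those tables.
- The case report form is not among the documents and may hold an ongoing indicator. If so, the SAP does not use it, and the summary it specifies would be the same.
- The size rests on assumptions. The 52% and 33% describe about 11 and 7 of 21 trial responders with selected mutations. The cohort also expects about 70 exon 20 insertions, for which the protocol reports lower benefit. Follow-up could be long, since afatinib was approved in 2013 and collection began in December 2019. Protocol section 9.7 also allows a second round of collection.
- If sites enter the duration to date, the median moves little in many scenarios. For the duration of treatment lines the SAP does cut at end of observation, although that rule does not govern this variable.
- The tables print N, so a gap between responders and contributors would be visible. It would not show whether the missing responses were ongoing or undocumented.

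A reader might also infer that Table 17-SEQ is biased, because it inherits the same summary. The documents do not support this: every eligible sequencing patient has moved from afatinib to osimertinib, so ongoing first-line responses are not expected. Likewise, in Table 24-UNC essentially only patients still on first line are exposed.

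**Conclusion.** The point holds for Tables 24-, 30- and 35-UNC and 19-SEQ. The plan specifies a summary that suits complete durations and applies it to a quantity that will be incomplete for some patients. The direction is certain if the data cut-off is independent of response duration. The size is not: the 19–31% ongoing, and the median of about 7–9 months (dropped) or about 11 months (cut) against 12, depend on the assumed response duration, onset and follow-up. The mean and upper quartile suffer more than the median when responses are cut at data collection.

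Two further inferences should not be drawn. One is that more recently available drugs, such as first-line osimertinib, would look worse than afatinib: no visible table gives duration of response by drug. The other is that the main results are compromised: response rate does not use this field, and time on treatment, time to second-line failure and overall survival are already censored and analysed by Kaplan-Meier.

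**What to change.** In Tables 24-, 30- and 35-UNC and 19-SEQ, replace the mean, SD and quartile summary of duration of response with Kaplan-Meier quartiles and 95% confidence intervals among responders, and report the number censored.

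The number-and-unit field cannot show by itself whether a response had ended, because the SAP cites no response start date. Send a data query for responders whose line was ongoing at end of observation or whose duration is blank, asking whether the response had ended or was ongoing, and its duration to date. Censor ongoing responses at the duration to end of observation.

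If the query cannot be answered, treat the recorded duration as censored when the line is still ongoing (EAD_treat_disc or OAD_treat_disc = No, or TREAT_ongoing = Yes). Report the number of responders with missing duration beside the table. Treatment status is only a stand-in, since a patient may stop for an adverse event while still responding, so the query comes first.

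The cost is a change to the SAP text, one derived status variable and a limited query. The upper quartile may not be estimable. The method is already in the SAP, and Tables 24-, 30- and 35-UNC were already revised in version 1.1.

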4.1.5 Time on treatment

Table 36-UNC. Time on treatment with index therapy EGFR-TKI (ELIGIBLE PATIENTS of the Uncommon Mutation Cohort) – Primary objective

The table will provide the Kaplan-Meier estimates of quartiles of time on treatment with index therapy EGFR-TKI (with their 95% Confidence Intervals, using Greenwood's variance estimate) (see "Computed variables" chapter).

Moreover, a Kaplan-Meier survival curve will be provided. The analysis will be represented on a plot having the time to event on the horizontal axis and the percentage of event-free patients on the vertical axis.

Table 37-UNC. Time to second-line treatment failure (ELIGIBLE PATIENTS of the Uncommon Mutation Cohort) – Secondary objective #4

The table will provide the Kaplan-Meier estimates of quartiles of time to second-line treatment failure (with their 95% Confidence Intervals, using Greenwood's variance estimate) (see "Computed variables" chapter).

Moreover, a Kaplan-Meier survival curve will be provided. The analysis will be represented on a plot having the time to event on the horizontal axis and the percentage of event-free patients on the vertical axis.

[figure not shown]
The analysis will be performed on ELIGIBLE PATIENTS in the cohort, considering only patients with Number of NSCLC treatment lines >1 (see "Computed variables" chapter) while excluding those with mutation T790M acquired only at second-line osimertinib start.

4.1.6 Overall Survival – Secondary objective #2

Table 38-UNC. Overall Survival with index therapy EGFR-TKI (ELIGIBLE PATIENTS of the Uncommon Mutation Cohort)

The table will provide the Kaplan-Meier estimates of quartiles of time to death (with their 95% Confidence Intervals, using Greenwood's variance estimate) (see algorithm for Overall Survival in the "Computed variables" chapter).

Moreover, a Kaplan-Meier survival curve will be provided. The analysis will be represented on a plot having the time to event on the horizontal axis and the percentage of event-free patients on the vertical axis.

4.2 SEQUENCING COHORT

4.2.1 Patient disposition, analysis sets and criteria violations

Table 1-SEQ. Patient disposition (ENROLLED PATIENTS of the Sequencing Cohort)

See corresponding table for the UNCOMMON MUTATION COHORT.

Figure 1-SEQ. Workflow of analysis sets and reasons for violations (ENROLLED PATIENTS of the Sequencing Cohort)

See corresponding figure for the UNCOMMON MUTATION COHORT.

Table 2-SEQ. Reasons for violations (ENROLLED PATIENTS of the Sequencing Cohort)

See corresponding table for the UNCOMMON MUTATION COHORT.

Table 3-SEQ. Duration of observation (ELIGIBLE PATIENTS of the Sequencing Cohort)

See corresponding table for the UNCOMMON MUTATION COHORT.

